8. PRESTUDY AND CONCOMITANT THERAPY

Prestudy therapies administered up to 7 days before first dose of study drug must be recorded at screening.

All subjects will receive supportive care according to local institution standards and applicable guidelines. While treatment guidelines and standards vary based on local practice and should be considered in the management of subjects, within the parameters of this study, it is recommended that supplemental oxygen can be administered or withdrawn, as appropriate, to maintain an SpO₂ \geq 93% as long as it is medically indicated (for subjects whose baseline SpO₂ is \geq 93% when clinically stable).

Concomitant therapies must be recorded throughout the study beginning with start of the first dose of study drug to the Day 28 visit (\pm 2 days). During hospitalization, concomitant medication will be recorded by the site staff in the eCRF. Upon discharge, parent(s)/caregiver(s) will be required to document use of concomitant medication in the electronic device in a medication log, which will serve as basis for recording in the eCRF by the site staff. Concomitant therapies should also be recorded beyond Day 28 in the subject's medical notes and reported by SAE forms (if applicable).

All therapies (prescription or over-the-counter medications, including vaccines, vitamins, herbal supplements, home oxygen therapy and non-pharmacologic therapies such as electrical stimulation, acupuncture, special diets, exercise regimens) different from the study drug must be recorded in the eCRF. Recorded information will include a description of the type of the drug/therapy, treatment phase, dose regimen, route of administration, and its indication.

Modification of an effective preexisting chronic therapy should not be made for the explicit purpose of entering a subject into the study; however, if a subject has received acute doses of a prohibited drug, switching to an alternative drug chosen at the discretion of the investigator should be allowed.

Concomitant medications are permitted as indicated for the management of study subjects with the exception of the medications noted here. The following medications are not permitted during the study and for the time period prior to randomization as noted:

- Moderate/strong inhibitors of OAT3: diclofenac, diflunisal, gemfibrozil, mycophenolic acid, piperacillin, probenecid, and teriflunomide (all within 24 hours prior to randomization).
- Systemic medications (either chronically [more than 14 days] or within 21 days prior to randomization), which are known to modulate the host's immune response or increase viral shedding, such as immunomodulatory therapies, except for systemic corticosteroids as noted below.
- Systemic corticosteroids are acceptable if they are taken acutely (14 days or less prior to randomization).
- Prescription medications intended to prevent or treat the RSV infection itself (eg, ribavirin, IV immunoglobulin, palivizumab), an investigational drug, an investigational vaccine, or use of an invasive investigational medical device within 30 days or 5 half-lives (whichever is longer) before the planned first dose of study drug. Prescription medications intended to treat the symptoms/sequelae of the RSV infection are permitted.
- Measles, mumps, and rubella (single or combination) vaccine within 1 week before screening, according to parent report.

The sponsor must be notified in advance (or as soon as possible thereafter) of any instances in which prohibited therapies are administered.

9. STUDY EVALUATIONS

9.1. Study Procedures

9.1.1. Overview

The [Time and Events Schedules](#) summarize the frequency and timing of efficacy, PK, biomarker, medical resource utilization, health economic, and safety measurements applicable to this study. There are 2 [Time and Events Schedules](#): 1 schedule for subjects who are hospitalized (up to their hospital discharge); 1 schedule for subjects after they are discharged from the hospital. Repeat or unscheduled samples may be taken for safety reasons or for technical issues with the samples.

The eCOA device will be provided to the parent(s)/caregiver(s) at screening to record the parent(s)/caregiver(s) ratings of the severity of the subject's symptoms (PRESORS) (see [Attachment 5](#)). The parent(s)/caregiver(s) will complete the eCOA twice daily (in the morning and in the evening); after Day 14, eCOA will be completed once daily in the evening (at approximately the same time each day) until the end of the study for subjects who have been discharged from the hospital. Whenever possible, the same parent(s)/caregiver(s) should

complete the eCOA throughout the study. The first parent/caregiver assessment on Day 1 needs to be recorded predose, before the LD. If the screening assessment was performed less than 8 hours prior to the LD, the predose assessment does not need to be performed. The first postdose parent/caregiver assessment must be performed between 6 and 12 hours after the LD (on Day 1 or Day 2, depending on the time of LD).

The investigator/study-site personnel will provide sufficient information to enable the parent(s)/caregiver(s) to complete the parent(s)/caregiver(s) eCOA and will ensure that the eCOA is completed correctly and on schedule to avoid missing or incorrect data.

Prior to completing the screening assessment, the parent(s)/caregiver(s) must complete a training module (included as part of the eCOA device) on how to enter responses to questions in the eCOA device. Study-site personnel will review the completion of the parent(s)/caregiver(s) eCOA on a daily basis.

The clinician eCOA ([Attachment 5](#)) will be completed by the investigator twice daily for the entire duration of hospitalization and once daily at the Day 7, Day 10, Day 14, and Day 28 visits during outpatient follow-up.

If multiple assessments are scheduled for the same timepoint, it is recommended that procedures be performed in the following sequence: noninvasive procedures should be collected first before invasive procedures (eCOA [parent/caregiver and clinician eCOA can be completed at the same time]; ECG first, then vital signs/SpO₂, then mid-turbinate nasal swab, with blood draw last). However, mid-turbinate nasal swabs for RSV viral load and blood collections for PK assessments should be kept as close to the specified time as possible. Other measurements may be done earlier than specified timepoints if needed. Actual dates and times of assessments will be recorded in the source documentation and eCRF. Electronic COA devices will automatically record the date and time of the eCOA assessments.

If treatment duration is extended up to 10 days, subjects will have an additional clinic visit 1 day (+2 days) after their last dose.

Medical resource utilization and health economics data will be collected. Refer to Section 9.6, Medical Resource Utilization and Health Economics, for details.

One additional PK assessment will be performed as indicated in the [Time and Events Schedules](#) for the first 9 subjects treated with the 60 mg/kg LD/40 mg/kg MD lumicitabine regimen if the Option A design (Section 3.1.1) is chosen and for the first 9 subjects in each cohort treated with the highest active lumicitabine regimen available in their respective cohort if the Option B design (Section 3.1.2) is chosen.

The results of clinical/safety evaluations that are performed as part of routine clinical care while hospitalized will be collected in the eCRF for viral, safety, and/or clinical evaluations.

9.1.2. Screening Phase

The procedures specified in the [Time and Events Schedules](#) will only be performed after the parent(s)/caregiver(s) written informed consent has been obtained.

Screening should be completed as soon as possible and the subject will be randomized within 5 days of RSV symptom onset to ensure the eligibility of the subject. Special attention should be paid to determine the duration of RSV symptoms from onset till time of randomization as accurately as possible. Procedures performed as part of standard of care within approximately 72 hours prior to randomization may be used in determining study eligibility or determining baseline values. The results of the safety laboratory tests performed at the local laboratory must be in accordance with Section 4, Subject Population. The investigator may consider the subject eligible if the previously abnormal laboratory test result is within normal range on a repeat testing in the local laboratory. Repeat testing is only allowed once.

During screening, 1 mid-turbinate nasal swab (if non-intubated) or 1 endotracheal sample (if intubated) will be collected and aliquoted for:

- RSV diagnosis using a PCR-based assay (at the local laboratory).
- RSV diagnosis confirmation using a PCR-based assay (at the central laboratory).
- Examination of viral and bacterial coinfection using multiplex PCR (at the central laboratory).
- Leftover mid-turbinate nasal swab samples will be stored and may be used for biomarker research if warranted.

9.1.3. Double-blind Treatment Phase

Day 1 (Day of Randomization and Loading Dose)

Eligible subjects will be randomized on Day 1. Study drug administration should start as soon as possible, but no later than 4 hours after randomization. Subjects will be dosed with a single oral LD on Day 1. Depending on the time of screening/enrollment, subjects will receive the first MD of study drug on Day 1. Subjects will receive no more than 2 doses per calendar day.

Assessments to be performed on Day 1 are specified in the [Time and Events Schedule](#). The mid-turbinate nasal swab (if non-intubated) or the mid-turbinate nasal swab and endotracheal sample (if intubated) should be taken as close as possible to and before the LD on Day 1.

Day 2 to Day 5/6 (End of Treatment)

Study drug administration continues until 10 doses have been taken unless treatment duration is extended. Subjects will receive 9 MDs without regard to food intake twice daily (at least 8 hours apart and maximum 16 hours apart, with no more than 2 doses per calendar day) through Day 5/6 (depending on the timing of the LD). The date and time of dose administration, the date and time of food intake (limited to the food ingested within 30 minutes before or after study drug administration), and the type of food will be recorded in the eCRF for hospitalized subjects. The subject may be discharged after Day 2 following completion of study procedures. Subjects may

also remain hospitalized if warranted by the subject's clinical status. In case the subject is discharged prior to the completion of treatment, study drug will continue to be administered at home by the parent(s)/caregiver(s) until all doses are administered. Instructions regarding study drug administration will be given to the parent(s)/caregiver(s) by the investigator or a qualified member of the study-site personnel.

Assessments will be performed as detailed in the [Time and Events Schedules](#). The parent(s)/caregiver(s) eCOA and the mid-turbinate nasal swabs (if non-intubated) (from the same nostril throughout the study) or endotracheal samples (if intubated) are to be taken once daily prior to study drug administration at approximately the same time each day. In case of nostril bleeding or irritation during the collection of a mid-turbinate nasal swab, all subsequent nasal swabs will be performed on the contralateral nostril. Should the study drug duration be increased to up to 10 days (following review of the data by the IDMC), samples will be taken every day up to and including 1 day (+2 days) following the last dose of study drug. Samples will be collected through Day 6 whether the subject is in hospital or has been discharged. In case mid-turbinate nasal swabs are collected at home, the subject's parent(s)/caregiver(s) should collect nasal swab specimens after being trained by the investigator/study-site personnel. Parent(s)/Caregiver(s) of subjects will be required to document the actual dates and times of collection of the nasal swab at home on the electronic device used for eCOA. Nasal swabs collected at home should be stored immediately between 2°C and 8°C (in the refrigerator) and brought to the site at the next visit.

Hospitalization duration will not be extended solely for study purposes. Telephone calls to parent(s)/caregiver(s) to facilitate compliance with study procedures between outpatient study visits are encouraged.

9.1.4. Posttreatment Phase (Follow-up)

Days 7 to 28

Subjects will be evaluated for a total of 28 days after randomization. If they are not hospitalized they will be required to return to the hospital for follow-up assessments as an outpatient on Day 7, Day 10, Day 14, and Day 28 as indicated in the [Time and Events Schedules](#). On Day 28 all subjects will complete the study either as an inpatient or outpatient.

Should the study drug duration be increased to up to 10 days (following review of the data by the IDMC, refer to Section [11.10](#), Independent Data Monitoring Committee), additional study drug may be provided if needed. If a subject is discontinued from study drug, a follow-up visit will be scheduled 2 days (+2 days), 5 days (+2 days), 9 days (+2 days), and 23 days (±2 days) after the last dose of study drug was administered. Assessments should be performed as indicated in the [Time and Events Schedules](#), respectively for the Day 7, Day 10, Day 14, and Day 28 visits.

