Vital signs	X	bid	bid	bid	bid	bid	bid	bid	bid	bid	bid

Phase Day	Screening 0	Treatment Phase			Follow-up Phase ^a							
		1	2	3 to 6 ^b	7 ^c (+2 days)	8 to 9	10 (+2days)	11 to 13	14 (+2 days)	15 to 27	28 (±2 days) EoS	
Study Procedure^d												
Nasal Swabs ^q												
Mid-turbinate nasal swab (if non-intubated) or endotracheal sample (if intubated): RSV diagnosis confirmation, viral and bacterial coinfection ^r	X											
Mid-turbinate nasal swab (if non-intubated) or mid-turbinate nasal swab and endotracheal sample (if intubated): RSV viral load, viral resistance (genome sequencing), biomarker, and infectious RSV viral load (plaque assay) ^s		X ^t	X	X	X		X		X			X
Clinical Laboratory Assessments												
Blood sampling for hematology ^u	X		X		X				X			
Blood sampling for biochemistry ^u	X				X				X			X
Urinalysis ^v	X			X					X			
Pharmacokinetics ^q												
Blood sampling for pharmacokinetics	Day 1 to Day 2											
		Post Dose 1	Post Dose 2									
		0.25 - 2h	0.5 - 1h 7h (±4)									
Group X ^w :		X	(X) ^x		X							
Group Y ^w :		X		(X) ^x	X							
Ongoing Subject Review												
Prior and Concomitant therapy	X	X	X	X	X	X	X	X	X	X	X	X
Adverse events	X	X	X	X	X	X	X	X	X	X	X	X

Abbreviations: bid: twice daily; ECG: electrocardiogram; eCOA: electronic clinical outcome assessment; eCRF: electronic case report form; EoS: end of study; IDMC: Independent Data Monitoring Committee; LD: loading dose; MD: maintenance dose; PK: pharmacokinetic(s); Q4h: every 4 hours; Q8h: every 8 hours; RSV: respiratory syncytial virus; SpO₂: peripheral capillary oxygen saturation.

Footnotes:

- a. If a subject is discontinued from study drug, a follow-up visit will be scheduled 2 days (+2 days), 5 days (+2 days), 9 days (+2 days), and 23 days (± 2 days) after the last dose of study drug was administered. Assessments should be performed as indicated in the Time and Events Schedule, respectively for the Day 7, Day 10, Day 14, and Day 28 visit.
- b. The subject may be discharged after Day 2 study procedures, but may also remain hospitalized if deemed appropriate by the investigator. Hospitalization duration will not be extended solely for study purposes.
- c. If treatment duration is increased to up to 10 days, then all assessments performed on Day 7 will again be performed 1 day (+2 days) after administration of the last MD.

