9.2. Efficacy Evaluations

Viral Load Determination

As an evaluation of antiviral activity of lumicitabine, RSV viral load will be measured in mid-turbinate nasal swabs (obtained from non-intubated subjects) or in mid-turbinate nasal

swabs and endotracheal samples (obtained from intubated subjects or via suction through tracheostomy or other sampling methods) using qRT-PCR performed at the central laboratory. Samples for the determination of RSV viral load will be taken as close as possible and before the LD on Day 1 and once daily at approximately the same time each day prior to study drug administration between Day 2 and Day 6 (whether hospitalized or not), and at the Day 7, Day 10, Day 14, and Day 28 visits. For each subject, the different mid-turbinate nasal swabs should be collected from the same nostril. However, in case of nostril bleeding or irritation during the collection of a mid-turbinate nasal swab, all subsequent nasal swabs will be performed on the contralateral nostril.

Quantitative culture of RSV using plaque assay may be performed centrally at timepoints selected by the virologist.

Should the study drug duration be increased to up to 10 days (following review of the data by the IDMC), 1 mid-turbinate nasal swab (if non-intubated) or 1 mid-turbinate nasal swab and 1 endotracheal sample (if intubated) will be taken every day, at approximately the same time, up to and including 1 day (+2 days) following the last dose of study drug.

Viral L-gene Sequencing for Viral Resistance

Viral sequencing analysis will be performed by sequencing the polymerase L-gene and other regions of the RSV genome (if warranted) in samples taken before treatment (at baseline), during treatment, and posttreatment, to identify preexisting sequence polymorphisms and to characterize emerging RSV variants.

The L-gene will be sequenced pretreatment in all subjects and postbaseline in subjects not achieving viral suppression. The sequencing of postbaseline samples may be triggered at the discretion of the sponsor's virologist, based on the changes in RSV viral load observed in each individual subject and the limits of the sequencing assay and taking into account the limits of the sequencing assay. The impact of newly identified mutations on in vitro antiviral activity of lumicitabine will be assessed.

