2. GENERAL ANALYSIS DEFINITIONS

2.1. Visit Windows and Phase Definition

Figure 1: Schematic Study Overview: Option A

Abbreviations: LD: loading dose; MD: maintenance dose; RSV: respiratory syncytial virus.

- a. Subjects randomized to placebo will be subsequently randomized in a 1:1 ratio to the placebo regimen matching Regimen A or Regimen B.

Phases will be constructed as follows:

Trial phase	Start date	End date
Pre-screening	Date time of first assessment, taken as part of standard of care within 84 hours* prior to randomization	1 minute before start of screening phase
Screening	00:00 of the date of signing the informed consent	1 minute before the first study medication intake
Treatment	Date time of first study medication intake	Date time of last investigational medication intake + 72 hours
Follow-up	End of Treatment phase + 1 minute	Trial termination date (date of last contact) with timestamp 23:59.

*In order to account for “approximately” 72 hours prior to randomization

The last phase, whichever it is for a subject, always ends on 23:59 of the day of trial termination (last contact) in study 64041575RSV2004. Note a subject can volunteer for long-term follow-up, in this case the subject will be enrolled in study 64041575RSV2002.

Assessments will be assigned to phases based on their date time, seconds will be ignored. If the day part of the start date of the assessment is present but the time part is missing, the assessment will be allocated as if it started at 00:00h on the day of the assessment (unless for Adverse Events see details in section 6.1.1). If the day part of the end date of the assessment is present but the time part is missing, no formal imputation will be done, but these rules will only be applied in order to be able to allocate assessments to phases. The assessment will be allocated as if it happened at 23:59h on the day of the assessment.

As subjects do not always adhere to the protocol visit schedule, the following rules are applied to assign actual visits to analysis visits. Listed below are the visit windows and the target days for each visit.

All visits (regardless the investigated parameter) will be allocated to analysis visits based on the day relative to the start of study medication:

Target Day	Analysis visit (numeric version)	Analysis visit	Day Interval
$-\infty$	-1	Screening	≤ 1 ¹
1	0	Baseline	≤ 1 ²
1	1	Day 1	[1] ³
2	2	Day 2	[2]
3	3	Day 3	[3]
4	4	Day 4	[4]
5	5	Day 5	[5]
6	6	Day 6	[6]
7	7	Day 7	[7,9]

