10	10	Day 10	[10,12*]
14	14	Day 14	[12*,20]
$+\infty$	28	Day 28	[21, $+\infty$ [

¹ Records before the datetime of first intake only.

² As calculated according to the baseline definition.

³ Includes only the post-dose records.

* Depending on the VISIT label, the measurement of subjects returning on Day 12 should be assigned to Day 10 or Day 14. In case the VISIT label equals Day 12 the measurement will be allocated to Day 10.

For the analyses of measurements scheduled once daily the following rules will be applied in order to have only one evaluation per subject per analysis visit:

1. If two assessments fall within the same interval, the measurement closest to the target day will be used.
2. If the assessments are equidistant, the last measurement within the interval will be used.
3. If there are two measurements on the same date and time, then the measurement with the highest sequence number will be used.

An exception will be made:

1. In case multiple nasal swabs were taken on a single day, the maximum viral load on the log scale will be used as the analysis value for that subject on that day.

For the analysis of measurements scheduled more than once daily (vital signs: twice daily and SpO₂: every 4 hours / every 8 hours), the assessments will be allocated to analysis time points as described in the table below based on the actual time of the measurement. In case there is more than one assessment per analysis time point window, the mean of these assessments will be calculated in order to have only one evaluation per analysis timepoint.

Analysis time point (numeric version)	Analysis time point	Time Interval (hour:min)
Vital sign assessments *		
1	Morning]02:00, 14:00]
2	Evening]14:00, 02:00]
SpO ₂ **		
0	Morning]0:00, 08:00]
8	Midday]08:00, 16:00]
16	Evening]16:00, 0:00]

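### After study drug is stopped, the protocol counts follow-up visits from the last dose and the SAP counts them from the first, so a last dose on Day 1 to 4 leaves a Day 10 or Day 14 window empty at nominal timing

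*Protocol*

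**What the plan says.** Protocol 9.1.4: "If a subject is discontinued from study drug, a follow-up visit will be scheduled 2 days (+2 days), 5 days (+2 days), 9 days (+2". The last of the four visits is set at "23 days (±2 days) after the last dose of study drug was administered". Footnote a of both Time and Events Schedules repeats the rule and adds: "Assessments should be performed as indicated in the Time and Events Schedule, respectively for the Day 7, Day 10, Day 14, and Day 28 visit". So a visit timed from the last dose carries a label timed from the first. The same section opens with "Subjects will be evaluated for a total of 28 days after randomization".

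SAP 2.1 uses the other clock: "All visits (regardless the investigated parameter) will be allocated to analysis visits based on the day relative to the start of study medication". Days 2 to 6 are single-day windows, Day 7 is [7,9], Day 10 is [10,12], Day 14 is [12,20], and Day 28 is Day 21 or later. The visit label matters only on the shared boundary: "Depending on the VISIT label, the measurement of subjects returning on Day 12 should be assigned to Day 10 or Day 14".

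On daily swabs, Protocol 9.1.3 says "Samples will be collected through Day 6 whether the subject is in hospital or has been discharged", and 9.2 asks for them "once daily at approximately the same time each day prior to study drug administration between Day 2 and Day 6 (whether hospitalized or not"). Protocol 10.2 does not treat stopping drug as withdrawal; families are encouraged to continue assessments under the same schedules. The SAP 5.2.3 model uses Days 2 to 7, and SAP 5.2.1 leaves missing swabs unimputed under missing at random.

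**The concern.** Efficacy is analysed in the ITT-i set, as randomised, on a clock that starts at the first dose. A child who stops drug early should therefore contribute viral load on the same study days as every other child. The last-dose rule shifts that child's later visits forward, so some analysis windows receive two visits' worth of attention and others none.

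Stopping happens after randomisation and can depend on arm: Grade 2 or higher rash, the liver criterion and attributed clinically significant adverse events all require discontinuation. Gaps created by the visit rule would fall only in children who stopped. The protocol is also not explicit about whether the daily swabs behind the primary endpoint go on once there is no further dose to time them against.

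**Working it through.** **1. Where the clocks agree.** With last dose on Day L, visits fall on L+2, L+5, L+9 and L+23. For L = 5 this gives 7, 10, 14 and 28, exactly the labels. No other L does.

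**2. Mapping at nominal timing.** Each visit day is placed in the SAP 2.1 windows; a Day 12 visit labelled Day 14 goes to Day 14.

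| L | Visit days | SAP windows entered | Empty among 7, 10, 14 |
|---|---|---|---|
| 1 | 3, 6, 10, 24 | 3, 6, 10, 28 | 7 and 14 |
| 2 | 4, 7, 11, 25 | 4, 7, 10, 28 | 14 |
| 3 | 5, 8, 12, 26 | 5, 7, 14, 28 | 10 |
| 4 | 6, 9, 13, 27 | 6, 7, 14, 28 | 10 |
| 5 | 7, 10, 14, 28 | 7, 10, 14, 28 | none |
| 6 | 8, 11, 15, 29 | 7, 10, 14, 28 | none |

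**3. Using the allowed +2 days.**
- L = 1: the L+5 visit can reach only Day 8, and L+9 spans Days 10 to 12. One visit cannot fill both Day 10 and Day 14.
- L = 2: L+5 reaches only Day 9, and L+9 spans Days 11 to 13. Again never both.
- L = 3: L+5 spans Days 8 to 10, so both are filled in 1 of 3 equally counted timings.
- L = 4: L+5 spans Days 9 to 11, so both are filled in 2 of 3.
- Off-nominal timing can also leave Day 7 without a visit for L = 3, 4 or 6.

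**4. Primary AUC.** The SAP contrast, after its divisor of 4, weights Days 2 to 6 by 1 each and Day 7 by 0.5, total 5.5. Share of weight observed, with swabs up to Day L assumed taken:

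| L | Daily swabs continue to Day 6 | Daily swabs stop with drug |
|---|---|---|
| 1 | 5/5.5 = 91% | Days 3, 6: 2/5.5 = 36% |
| 2 | 100% | Days 2, 4, 7: 2.5/5.5 = 45% |
| 3 | 100% | Days 2, 3, 5, 7: 3.5/5.5 = 64% |
| 4 | 100% | Days 2, 3, 4, 6, 7: 4.5/5.5 = 82% |
| 5 | 100% | Days 2 to 5, 7: 4.5/5.5 = 82% |
| 6 | 100% | 100% |

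**5. Secondary AUCs.** The SAP does not print these contrasts. Assume that the same trapezoidal weights are extended and that daily swabs continue. To Day 10, Day 7 weighs 0.5 + 1.5 = 2 and Day 10 weighs 1.5, total 5 + 2 + 1.5 = 8.5. To Day 14, Day 10 weighs 1.5 + 2 = 3.5 and Day 14 weighs 2, total 5 + 2 + 3.5 + 2 = 12.5. At nominal timing:
- L = 1 keeps 6.5/8.5 = 76% to Day 10 and 8.5/12.5 = 68% to Day 14.
- L = 2 keeps 100% and 10.5/12.5 = 84%.
- L = 3 or 4 keeps 7/8.5 = 82% and 9/12.5 = 72%.

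**6. Final visit.** L+23 gives Days 24, 25, 26 and 27 for L = 1 to 4. Against Day 28 ±2 (Days 26 to 30), Days 24 and 25 are outside and Days 26 and 27 inside. All fall in the SAP Day 28 window.

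**7. Power.** The stated figure of about 97% for 180 children is reproduced to within a point: a simulation of the two contrasts with Pocock spending and looks assumed at 90, 120 and 180 gives 96.2%. The finding does not depend on it. No change in power can be computed without a discontinuation rate.

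**The case against.** Footnote a is attached to the Follow-up Phase heading, so by its position it does not replace the Treatment Phase columns. Sections 9.1.3 and 9.2 and the swab footnotes set daily sampling by study day through Day 6, at home or in hospital. A reader might infer that the primary Day 2 to 7 swabs are lost in children who stop; the documents do not show that. They leave only an unwritten sentence, and the 36% to 82% figures need the less natural reading.

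Binning by actual day is right for an AUC that starts at first dose. Swabs are analysed at their true time, not discarded. The trapezoidal sensitivity AUCs use actual sampling times and interpolate across the gaps.

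A reader might also infer that every child who stops is affected. A last dose on Day 5 or 6 leaves no window empty at nominal timing. Nor does missingness related to treatment by itself break missing at random, since treatment, visit and baseline viral load are in the model; nothing in the documents shows dependence on unobserved viral load.

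Finally, counting from the last dose has an evident purpose: it gives early stoppers the post-exposure follow-up of a child whose last dose was on Day 5. All of this stands. It limits the finding but does not remove the conflict between Protocol 9.1.4 and SAP 2.1, or between 9.1.4 and its own 28 days.

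**Conclusion.** The two documents use different clocks after drug is stopped and must be reconciled. For a last dose on Day 1 to 4 at nominal timing, the Day 10 or Day 14 window is empty, and Day 7 as well for Day 1. For a last dose on Day 1 or 2, no permitted timing fills both Day 10 and Day 14. The effect falls mainly on the secondary AUCs to Day 10 and Day 14 and on by-visit summaries.

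The primary AUC is little affected provided daily swabs continue, which the protocol indicates but does not state for a child off drug. The 28-day conflict is real but small: only the nominal Days 24 and 25 lie outside the visit window. These results assume on-target visits except where the windows are used explicitly. The number of children involved, and hence any bias or loss of power, cannot be sized from the documents. The change is worth making because it is cheap and settles the sampling question before it reaches sites.

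**What to change.** Amend Protocol 9.1.4 and footnote a of both schedules to say that stopping study drug does not change the viral-load and efficacy schedule. Daily swabs continue through Day 6, by caregivers if the child has been discharged, and the Day 7, 10, 14 and 28 efficacy assessments stay counted from first dose. At nominal timing this fills each of those windows for any stopping day.

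Reconcile any safety follow-up tied to the last dose with 9.1.4 and SAP 2.1, including how such visits are labelled and allocated. Its timing is for the sponsor to decide.

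The cost is one footnote and one paragraph in an amendment, a few more home swabs, and possibly an extra contact in children who stop.
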